10. QUALITY CONTROL AND QUALITY ASSURANCE

During study conduct, Pfizer or its agent will conduct periodic monitoring visits to ensure that the protocol and Good Clinical Practices (GCPs) are being followed. The monitors may review source documents to confirm that the data recorded on CRFs is accurate. The investigator and institution will allow Pfizer monitors or its agents and appropriate regulatory authorities direct access to source documents to perform this verification.

The study site may be subject to review by the Institutional Review Board (IRB)/Independent Ethics Committee (IEC), and/or to quality assurance audits performed by Pfizer, or companies working with or on behalf of Pfizer, and/or to inspection by appropriate regulatory authorities.

It is important that the investigator(s) and their relevant personnel are available during the monitoring visits and possible audits or inspections and that sufficient time is devoted to the process.

11. DATA HANDLING AND RECORD KEEPING

11.1. Case Report Forms/Electronic Data Record

As used in this protocol, the term CRF should be understood to refer to either a paper form or an electronic data record or both, depending on the data collection method used in this study.

A CRF is required and should be completed for each included subject. The completed original CRFs are the sole property of Pfizer and should not be made available in any form to third parties, except for authorized representatives of Pfizer or appropriate regulatory authorities, without written permission from Pfizer.

The investigator has ultimate responsibility for the collection and reporting of all clinical, safety and laboratory data entered on the CRFs and any other data collection forms (source documents) and ensuring that they are accurate, authentic / original, attributable, complete,

consistent, legible, timely (contemporaneous), enduring and available when required. The CRFs must be signed by the investigator or by an authorized staff member to attest that the data contained on the CRFs is true. Any corrections to entries made in the CRFs, source documents must be dated, initialed and explained (if necessary) and should not obscure the original entry.

In most cases, the source documents are the hospital's or the physician's subject chart. In these cases data collected on the CRFs must match the data in those charts.

In some cases, the CRF, or part of the CRF, may also serve as source documents. In these cases, a document should be available at the investigator's site as well as at Pfizer and clearly identify those data that will be recorded in the CRF, and for which the CRF will stand as the source document.

11.2. Record Retention

To enable evaluations and/or audits from regulatory authorities or Pfizer, the investigator agrees to keep records, including the identity of all participating subjects (sufficient information to link records, eg, CRFs and hospital records), all original signed informed consent documents, copies of all CRFs, safety reporting forms, source documents, and detailed records of treatment disposition, and adequate documentation of relevant correspondence (eg, letters, meeting minutes, telephone calls reports). The records should be retained by the investigator according to International Conference on Harmonisation (ICH), local regulations, or as specified in the Clinical Study Agreement (CSA), whichever is longer.

If the investigator becomes unable for any reason to continue to retain study records for the required period (eg, retirement, relocation), Pfizer should be prospectively notified. The study records must be transferred to a designee acceptable to Pfizer, such as another investigator, another institution, or to an independent third party arranged by Pfizer.

Investigator records must be kept for a minimum of 15 years after completion or discontinuation of the study or for longer if required by applicable local regulations.

The investigator must obtain Pfizer's written permission before disposing of any records, even if retention requirements have been met.

12. ETHICS

12.1. Institutional Review Board (IRB)/Independent Ethics Committee (IEC)

It is the responsibility of the investigator to have prospective approval of the study protocol, protocol amendments, informed consent documents, and other relevant documents, eg, recruitment advertisements, if applicable, from the IRB/IEC. All correspondence with the IRB/IEC should be retained in the Investigator File. Copies of IRB/IEC approvals should be forwarded to Pfizer.

The only circumstance in which an amendment may be initiated prior to IRB/IEC approval is where the change is necessary to eliminate apparent immediate hazards to the subjects. In that event, the investigator must notify the IRB/IEC and Pfizer in writing immediately after the implementation.

12.2. Ethical Conduct of the Study

The study will be conducted in accordance with legal and regulatory requirements, as well as the general principles set forth in the International Ethical Guidelines for Biomedical Research Involving Human Subjects (Council for International Organizations of Medical Sciences 2002), Guidelines for GCP (ICH 1996), and the Declaration of Helsinki (World Medical Association 1996, 2008).

In addition, the study will be conducted in accordance with the protocol, the International Conference on Harmonization guideline on Good Clinical Practice, and applicable local regulatory requirements and laws.

12.3. Subject Information and Consent

All parties will ensure protection of subject personal data and will not include subject names on any sponsor forms, reports, publications, or in any other disclosures, except where required by laws.

Subject names, address, birth date and other identifiable data will be replaced by a numerical code consisting of a numbering system provided by Pfizer in order to de-identify the trial subject. In case of data transfer, Pfizer will maintain high standards of confidentiality and protection of subject personal data.

The informed consent document must be in compliance with ICH GCP, local regulatory requirements, and legal requirements.

The informed consent document used in this study, and any changes made during the course of the study, must be prospectively approved by both the IRB/IEC and Pfizer before use.

The investigator must ensure that each study subject, or his/her legal representative, is fully informed about the nature and objectives of the study and possible.

The investigator, or a person designated by the investigator, will obtain written informed consent from each subject or the subject's legal representative before any study-specific activity is performed. The investigator will retain the original of each subject's signed consent document.

12.4. Reporting of Safety Issues and Serious Breaches of the Protocol or ICH GCP

In the event of any prohibition or restriction imposed (ie, clinical hold) by an applicable Competent Authority in any area of the World, or if the investigator is aware of any new information which might influence the evaluation of the benefits and risks of the investigational product, Pfizer should be informed immediately.

In addition, the investigator will inform Pfizer immediately of any urgent safety measures taken by the investigator to protect the study subjects against any immediate hazard, and of any serious breaches of this protocol or of ICH GCP that the investigator becomes aware of.

13. DEFINITION OF END OF TRIAL

13.1. End of Trial in a Member State

End of Trial in a Member State of the European Union is defined as the time at which it is deemed that sufficient subjects have been recruited and completed the study as stated in the regulatory application (ie, Clinical Trial Application (CTA)) and ethics application in the Member State. Poor recruitment (recruiting less than the anticipated number in the CTA) by a Member State is not a reason for premature termination but is considered a normal conclusion to the study in that Member State.

13.2. End of Trial in all Participating Countries

End of Trial in all participating countries is defined as last subject last visit.

14. SPONSOR DISCONTINUATION CRITERIA

Premature termination of this study may occur because of a regulatory authority decision, change in opinion of the IRB/IEC, drug safety problems, or at the discretion of Pfizer. In addition, Pfizer retains the right to discontinue development of tofacitinib at any time.

If a study is prematurely terminated or discontinued, Pfizer will promptly notify the investigator. After notification, the investigator must contact all participating subjects and the hospital pharmacy (if applicable) within 1 week. As directed by Pfizer, all study materials must be collected and all CRFs completed to the greatest extent possible.

15. PUBLICATION OF STUDY RESULTS

15.1. Communication of Results by Pfizer

Pfizer fulfills its commitment to publicly disclose clinical trial results through posting the results of studies on www.clinicaltrials.gov (ClinicalTrials.gov), the European Clinical Trials Database (EudraCT), and/or www.pfizer.com, and other public registries in accordance with applicable local laws/regulations.

In all cases, study results are reported by Pfizer in an objective, accurate, balanced, and complete manner and are reported regardless of the outcome of the study or the country in which the study was conducted.

www.clinicaltrials.gov

Pfizer posts clinical trial US Basic Results on www.clinicaltrials.gov for Pfizer-sponsored interventional studies conducted in patients that evaluate the safety and/or efficacy of a Pfizer product, regardless of the geographical location in which the study is conducted. US Basic Results are submitted for posting within 1 year of the primary completion date for studies in

adult populations or within 6 months of the primary completion date for studies in pediatric populations.

Primary completion date is defined as the date that the final subject was examined or received an intervention for the purposes of final collection of data for the primary outcome, whether the clinical study concluded according to the prespecified protocol or was terminated.

EudraCT

Pfizer posts EU Basic Results on EudraCT for all Pfizer-sponsored interventional studies that are in scope of EU requirements. EU Basic Results are submitted for posting within 1 year of the primary completion date for studies in adult populations or within 6 months of the primary completion date for studies in pediatric populations.

www.pfizer.com

Pfizer posts Public Disclosure Synopses (clinical study report synopses in which any data that could be used to identify individual patients has been removed) on www.pfizer.com for Pfizer-sponsored interventional studies at the same time the US Basic Results document is posted to www.clinicaltrials.gov.

15.2. Publications by Investigators

Pfizer supports the exercise of academic freedom and has no objection to publication by principal investigator of the results of the study based on information collected or generated by principal investigator, whether or not the results are favorable to the Pfizer product. However, to ensure against inadvertent disclosure of confidential information or unprotected inventions, the investigator will provide Pfizer an opportunity to review any proposed publication or other type of disclosure of the results of the study (collectively, "Publication") before it is submitted or otherwise disclosed.

The investigator will provide any publication to Pfizer at least 30 days before they are submitted for publication or otherwise disclosed. If any patent action is required to protect intellectual property rights, the investigator agrees to delay the disclosure for a period not to exceed an additional 60 days.

The investigator will, on request, remove any previously undisclosed confidential information before disclosure except for any study- or Pfizer product-related information necessary to the appropriate scientific presentation or understanding of the study results.

If the study is part of a multi-centre study, the investigator agrees that the first publication is to be a joint publication covering all study sites, and that any subsequent publications by the principal investigator will reference that primary publication. However, if a joint manuscript has not been submitted for publication within 12 months of completion or termination of the study at all participating sites, the investigator is free to publish separately, subject to the other requirements of this section.

For all publications relating to the study, the institution will comply with recognized ethical standards concerning publications and authorship, including Section II - “Ethical Considerations in the Conduct and Reporting of Research” of the Uniform Requirements for Manuscripts Submitted to Biomedical Journals, <http://www.icmje.org/index.html#authorship>, established by the International Committee of Medical Journal Editors.

Publication of study results is also provided for in the CSA between Pfizer and the institution. In this section entitled [Publications by Investigators](#), the defined terms shall have the meanings given to them in the CSA.

If there is any conflict between the CSA and any Attachments to it, the terms of the CSA control. If there is any conflict between this protocol and the CSA, this protocol will control as to any issue regarding treatment of study subjects, and the CSA will control as to all other issues.

Appendix 1. Mayo Scoring System*

Stool frequency[†]:

0 = Normal no. of stools for this patient
1 = 1 to 2 stools more than normal
2 = 3 to 4 stools more than normal
3 = 5 or more stools more than normal
Subscore, 0 to 3

Rectal bleeding[‡]:

0 = No blood seen
1 = Streaks of blood with stool less than half the time
2 = Obvious blood with stool most of the time
3 = Blood alone passes
Subscore, 0 to 3

Findings on endoscopy:

0 = Normal or inactive disease
1 = Mild disease (erythema, decreased vascular pattern)
2 = Moderate disease (marked erythema, absent vascular pattern, any friability, erosions)
3 = Severe disease (spontaneous bleeding, ulceration)
Subscore, 0 to 3

Physician's global assessment[§]:

0 = Normal
1 = Mild disease
2 = Moderate disease
3 = Severe disease
Subscore, 0 to 3

* The Mayo score ranges from 0 to 12, with higher scores indicating more severe disease.⁹

† Each patient serves as his or her own control to establish the degree of abnormality of the stool frequency. Normal number of bowel movements represents the number of bowel movements when not having a flare.

‡ The daily bleeding score represents the most severe bleeding of the day.

§ The physician's global assessment acknowledges the three other criteria, the patient's recollection of abdominal discomfort and general sense of wellbeing, and other observations, such as physical findings and the patient's performance status.

Appendix 2. Prohibited Concomitant Medications

This is not an all inclusive list. Study personnel should stay current and consult with their pharmacy to exclude all concomitant medications that are either moderate to potent CYP3A inhibitors or inducers.

| Moderate to Potent CYP3A Inhibitors | Moderate to Potent CYP3A Inducers | Other Prohibited Medications |
|-------------------------------------|-----------------------------------|---|
| Amprenavir | Avasimibe# | Azathioprine |
| Amiodarone | Bosentan | 6-Mercaptopurine |
| Aprepitant | Barbiturates | Methotrexate |
| Atazanavir | Carbamazepine# | Cyclosporine |
| Boceprevir | Efavirenz | Mycophenolate mofetil /mycophenolic acid |
| Casopitant | Etravirine | Tacrolimus |
| Cimetidine | Mitotane# | Interferon |
| Ciprofloxacin | Modafinil | Infliximab |
| Clarithromycin# | Nafcillin | Adalimumab |
| | | Certolizumab |
| Cobicistat# | Phenobarbital# | Golimumab |
| Conivaptan# | Phenytoin# | Corticosteroids IV or PR |
| Darunavir | Rifabutin# | 5-ASA PR |
| | Rifampin# | Natalizumab, vedolizumab, and other anti-adhesion molecule therapy (including investigational agents) |
| Diethyldithiocarbamate | St. John's Wort# | Leukocyte apheresis including selective lymphocyte, monocyte or granulocyte apheresis (eg, Cellsorba®) or plasma exchange |
| Diltiazem | | Other immunosuppressants |
| Dronedarone | Talviraline | Other biologics with immunomodulatory properties |
| Elvitegravir# | | |
| Erythromycin | | |
| Fluconazole | | |
| Fluvoxamine | | |
| Imatinib | | |
| Indinavir# | | |
| Itraconazole# | | |
| Ketoconazole# | | |
| Lopinavir# | | |
| Mibefradil# | | |
| Mifepristone (RU486) | | |
| Nefazodone# | | |
| Nelfinavir# | | |
| Norfloxacin | | |
| Posaconazole# | | |
| Ritonavir# | | |
| Saquinavir# | | |
| Schisandra sphenanthera | | |

| | | |
|-----------------|--|--|
| Telaprevir | | |
| Telithromycin# | | |
| Tipranavir# | | |
| Tofisopam | | |
| Troleandomycin# | | |
| Verapamil | | |
| Voriconazole# | | |

Notated as potent inhibitors or inducers

It is recommended that subjects avoid consumption of grapefruit juice exceeding 8 ounces (~240 mL) total in a day while in the study.

In a situation where appropriate medical care of a subject requires the use of a prohibited CYP3A inhibitor or inducer: Potent inhibitors and inducers of CYP3A are not permitted in the study **EXCEPT** in emergency situations requiring no more than one day of administration. *Note: Mitotane (half-life of 18-159 days) is not permitted for any duration due to its long half-life.* Subjects may be initiated on moderate inhibitors (except amiodarone) and moderate inducers (shown above), as required, if the total duration of treatment lasts less than or equal to 7 days. If a subject requires multiple courses of treatment with a prohibited medication as described above, the investigator should contact the sponsor to discuss the suitability of the subject to remain in the study. Topical (including skin or mucous membranes) application of antibacterial and antifungal medications is permitted.

Appendix 3. Guidelines for Monitoring and Discontinuations

The following laboratory abnormalities require monitoring and re-testing ideally within 3-5 days:

- Absolute neutrophil count $<1.2 \times 10^9/L$ ($<1200/mm^3$).
- Absolute lymphocyte count $<0.5 \times 10^9/L$ ($<500/mm^3$).
- Any single hemoglobin value <8.0 g/dL, or any decrease in hemoglobin >2.0 g/dL from baseline.
- Platelet count $<100 \times 10^9/L$ ($<100,000/mm^3$).
- An increase in serum creatinine of $>50\%$ from the baseline value; OR an absolute increase in serum creatinine >0.5 mg/dL (>44.2 umol/L) from baseline value.
- Any single AST and/or ALT elevation ≥ 3 times the upper limit of normal (repeat laboratory testing should include albumin, creatine kinase, total bilirubin, direct and indirect bilirubin, GGT, PT [prothrombin time] with INR [international normalized ratio], and alkaline phosphatase), regardless of the total bilirubin. (Please note that 3 times the upper limit of normal increases in ALT, AST need confirmation on separate blood draw before undertaking thorough evaluation for liver injury).
- Any creatine kinase (CK) >10 times the upper limit of normal (repeat laboratory testing should also include cardiac troponin).
- For women of child-bearing potential with any positive urine β -hCG test, the subject will have study drug interrupted and a serum sample submitted to the central laboratory for β -hCG testing.

Additional individual subject safety monitoring in addition to these guidelines is at the discretion of the investigator and dependent on any perceived safety concerns. Unscheduled laboratory testing through the central laboratory may be obtained at any time during the study to assess such concerns, and a subject may be withdrawn at any time at the discretion of the investigator.

Treatment with tofacitinib will be discontinued and the subject withdrawn from this study for:

- Serious infections defined as any infection (viral, bacterial, and fungal) requiring parenteral antimicrobial therapy, hospitalization for treatment, or meeting other criteria that require the infection to be classified as serious adverse event.

- Two sequential absolute neutrophil counts $<0.75 \times 10^9/L$ ($<750/mm^3$).

- Two sequential absolute lymphocyte counts $<0.5 \times 10^9/L$ ($<500/mm^3$).
- Two sequential hemoglobin <8.0 g/dL or a decrease of $>30\%$ from baseline.
- Two sequential platelet counts $<75 \times 10^9/L$ ($<75,000/mm^3$).
- Two sequential increases in serum creatinine $>50\%$ over the baseline value AND an absolute increase in serum creatinine >0.5 mg/dL (>44.2 umol/L).
- Two sequential AST or ALT elevation ≥ 3 times the upper limit of normal with at least one total bilirubin value ≥ 2 times the upper limit of normal.^a
- Two sequential AST or ALT elevation ≥ 3 times the upper limit of normal accompanied by signs or symptoms consistent with hepatic injury.^a
- Two sequential AST or ALT elevation ≥ 5 times the upper limit of normal, regardless of total bilirubin or accompanying signs or symptoms.^a
- Two sequential CK elevations >10 times the upper limit of normal, unless the causality is known not to be medically serious (eg, exercise induced).
- Female subjects found to be pregnant during the study.
- Initiation of a new treatment for UC.
- Surgery for UC.
- Other serious or severe AEs, after consultation with the Pfizer medical monitor or designee.

C
C
I

- a In each case, there is a need for additional investigations, such as review of ethanol, recreational drug and dietary supplement consumption; testing for acute hepatitis A, B or C infection and biliary tract imaging should be promptly discussed with the Pfizer medical monitor or designee.

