Due to the design of the study, there will be no formal hypothesis testing. Descriptive summary statistics such as number, percentage for categorical endpoints and mean, standard deviation, median for continuous endpoints will be summarized by the following four subgroups of subjects based on the status at baseline of Study A3921139: 1) in remission defined by a total Mayo score ≤ 2 with no individual subscore > 1 , and rectal bleeding subscore of 0, 2) treatment failure defined by an increase in Mayo score of at least 3 points from baseline value of the maintenance study (A3921096), accompanied by an increase in rectal bleeding subscore by at least 1 point, and an increase of endoscopic subscore of at least 1 point (yielding an absolute endoscopic subscore of ≥ 2), 3) all other subjects from maintenance study A3921096 neither in remission nor fulfilling the definition of treatment failure, and 4) non-responders from induction studies A3921094 or A3921095.

Safety Analysis

The safety data will be summarized in accordance with Pfizer Data Standards based on the safety analysis set defined as all subjects who receive at least 1 dose of study medication.

SCHEDULE OF ACTIVITIES

The Schedule of Activities table provides an overview of the protocol visits and procedures. Refer to Study Procedures ([Section 6](#)) and Assessments ([Section 7](#)) for detailed information on each procedure and assessment required for compliance with the protocol.

All study visits during the first year will have a window of ± 5 days. The 4-week follow-up evaluation visit and all study visits in subsequent years will have a window of ± 7 days.

This study will continue until approximately July 2020. Individual subject duration of participation will vary depending on when the subject was enrolled into the study and the end date of approximately July 2020. Therefore, the duration of participation for an individual subject may range from approximately 4 years to more than 7 years. Annual schedule of activities are identical from year 4 and beyond. For illustration purposes, the [Schedule of Activities](#) contains study procedures up to Month 72 (year 6). If the study continues beyond year 6 for an individual subject, the investigator should continue to follow the same visit schedule and study procedures outlined during the study visits of year 4.

Schedule of activities for first year:

| Study Procedure | Baseline | Open Label Treatment Period | | | | | |

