For subjects receiving tofacitinib 10 mg BID, the tofacitinib dose may be adjusted to 5 mg BID if the subject meets any of the following laboratory criteria after they are repeated and confirmed within approximately 7 days:

- Any single hemoglobin value that drops >2 g/dL (>20 g/L) below baseline of Study A3921139.
- Absolute neutrophil count $<1.2 \times 10^9/L$ ($<1200/mm^3$).
- Absolute lymphocyte count $<0.75 \times 10^9/L$ ($<750/mm^3$).
- Platelet count $<100 \times 10^9/L$ ($<100,000/mm^3$).

In addition, for subjects receiving tofacitinib 10 mg BID, the tofacitinib dose may be adjusted to 5 mg BID if the subject is in remission (based on Mayo score) or in PMS remission at Month 24 or any visit beyond Month 24, after discussion with the sponsor. PMS remission is defined as a partial Mayo score ≤ 2 with no individual subscore >1 . If a subject experiences loss of response and flare after the dose reduction from 10 mg BID to 5 mg BID, the dose may be increased back to 10 mg BID. In this situation, loss of response is defined as an increase in partial Mayo score of at least 2 points from the time when the subject was in remission or PMS remission (ie, when the dose was reduced to 5 mg BID) for two consecutive visits (at least 2 weeks apart), accompanied by an increase in rectal bleeding subscore by at least 1 point from when the subject was in remission or PMS remission. If response is lost, endoscopy should be performed to determine if the subject is experiencing a flare. Flare, in this situation, is defined by an increase in Mayo score of at least 3 points from the time when the subject was in remission or PMS remission, accompanied by an increase in rectal bleeding subscore by at least 1 point, and an increase of endoscopic subscore of at least 1 point (unless the endoscopic subscore was a '3' and remains a '3').

Lastly, subjects receiving tofacitinib 10 mg BID and who are identified to have one or more of the risk factors for pulmonary embolism will need to reduce their tofacitinib dose to 5 mg BID.

Tofacitinib dose adjustments should be implemented at a scheduled study visit, unplanned study visit, or upon verification of laboratory abnormalities upon repeat testing. Subjects who meet the laboratory discontinuation criteria described in [Appendix 3](#) will be withdrawn from the study.

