9. APPENDICES

Appendix 1. Definition of Analysis Visit Windows

Analysis visit windows will be used for efficacy variables, and for any safety displays that display by visit.

Visit Label	Target Day	Analysis Visit window
Baseline	Day 1	Up to Day 1
Month 1	Day 30	Days 2-45
Month 2	Day 60	Days 46-90
Month 4	Day 120	Days 91-150
Month 6	Day 180	Days 151-225
Month 9	Day 270	Days 226-315
Month 12	Day 360	Days 316-405
Month 15	Day 450	Days 406-495
Month 18	Day 540	Days 496-585
Month 21	Day 630	Days 586-675
Month 24	Day 720	Days 676-765
Month 27	Day 810	Days 766-855
Month 30	Day 900	Days 856-945
Month 33	Day 990	Days 946-1035
Month 36	Day 1080	Days 1036-1125
Month 39	Day 1170	Days 1126-1215
Month 42	Day 1260	Days 1216-1305
Month 45	Day 1350	Days 1306-1395
Month 48	Day 1440	Days 1396-1485
Month 51	Day 1530	Days 1486-1575
Month 54	Day 1620	Days 1576-1665
Month 57	Day 1710	Days 1666-1755
Month 60	Day 1800	Days 1756-1845
Month 63	Day 1890	Days 1846-1935
Month 66	Day 1980	Days 1936-2025
Month 69	Day 2070	Days 2026-2115
Month 72	Day 2160	Day 2116-2205
Month 75	Day 2250	Days 2206-2295
Month 78	Day 2340	Days 2296-2385
Month 81	Day 2430	Days 2386-2475
Month \geq 84	Day 2520	Days \geq 2476

If more than one observation from the same subject falls into the same window, the value closest to the target day will be used as the observation for that analysis visit. All observations will, however, be included in the listings.

For efficacy endpoints derived based on total Mayo score we will use the same windows from the above table although total Mayo score was not assessed at each visit.

Some PRO data or laboratory data were not scheduled to be assessed at each visit. In this case, the unscheduled 'windowed' visit will be moved to the next scheduled windowed visit for analysis and reporting.

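### By-visit laboratory displays can swap an abnormal scheduled value for its re-test, because SAP Appendix 1 keeps the value closest to the target day and gives the scheduled draw no priority (minor)

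*Protocol*

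**What the plan says.** Three rules meet here.

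- **Re-tests.** Protocol Appendix 3 lists limits for neutrophils, lymphocytes, hemoglobin, platelets, creatinine, AST/ALT and CK under the line "The following laboratory abnormalities require monitoring and re-testing ideally within 3-5 days". For subjects on 10 mg BID, Protocol Section 5.8 makes a dose change possible "if the subject meets any of the following laboratory criteria after they are repeated and confirmed within approximately 7 days". Both are triggered by an abnormal result only.
- **Choice of value.** SAP Appendix 1: "Analysis visit windows will be used for efficacy variables, and for any safety displays that display by visit". And: "If more than one observation from the same subject falls into the same window, the value closest to the target day will be used". It gives the scheduled draw no priority, does not exclude repeats, and has no rule for ties. It adds: "All observations will, however, be included in the listings".
- **Visit timing.** Protocol Schedule of Activities: "All study visits during the first year will have a window of ± 5 days". Later visits have ±7 days.

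The last paragraph of SAP Appendix 1 moves unscheduled windowed results to the next scheduled visit, but only for data that are not assessed at every visit. Hematology and serum chemistry are drawn at every scheduled visit, so it does not help here. SAP Section 7.3 says only that safety data are summarized as observed. Neither SAP Section 6.2 nor Section 8.2.4 says whether the incidence of laboratory abnormalities uses windowed values or all values.

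**The concern.** The SAP windows are wide (±45 days from Month 12), so a scheduled draw and its re-test a few days later normally share one. Which of the two reaches the table then depends on whether the visit was early or late. Only subjects whose first value crossed a limit have an ordered second value, so the selection depends on the outcome. A flagged value tends to be followed by a less extreme one.

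Example: the Month 12 target is Day 360. A scheduled neutrophil count of 1.1 on Day 356 and a re-test of 1.6 on Day 360 enter the table as 1.6. With the same two results on Days 361 and 365, the table shows 1.1.

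Safety is the primary objective, and these analytes are among those the protocol names as changing on tofacitinib (Section 1.2). By-visit counts of abnormal values, shift tables and minima or maxima could therefore look milder than the scheduled samples were.

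**Working it through.** The plan gives no figure of its own on this point, so the rule is enumerated.

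**Inputs.** Re-test gap g = 3, 4 or 5 days (Protocol Appendix 3), or 7 days (Section 5.8). Visit tolerance ±5 days to Month 12 and ±7 days afterwards (Schedule of Activities). Target day 30 × m for Month m, baseline on Day 1 (SAP Appendix 1). Assumption: visits fall evenly on the allowed whole days.

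**1. When the re-test wins.** Let x be the scheduled draw day minus the target day. The re-test is used if |x + g| < |x|, that is, if x < −g/2. This means x ≤ −2 for g = 3, x ≤ −3 for g = 4 or 5, and x ≤ −4 for g = 7. For g = 4, x = −2 is a tie, which the SAP does not resolve; it is not counted as displaced.

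**2. 30-day months.** A visit 30m days after Day 1 falls on Day 30m + 1, one day after the target. So x runs from −4 to +6 (11 days) in year 1 and from −6 to +8 (15 days) later.

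| Gap | ±5 days | ±7 days |
|---|---|---|
| 3 | 3/11 = 27% | 5/15 = 33% |
| 4 or 5 | 2/11 = 18% | 4/15 = 27% |
| 7 | 1/11 = 9% | 3/15 = 20% |

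**3. Calendar months.** The nominal visit is s days after the target, where s = (days in the m months) + 1 − 30m. With ±5 days, the displaced days out of 11 number 4 − s for g = 3 and 3 − s for g = 4 or 5 (never below 0). Take a 365-day year and weight the 12 starting months equally, so the denominator is 12 × 11 = 132.

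| Visit | s (number of starting months) | g = 3 | g = 4 or 5 |
|---|---|---|---|
| Month 1 | −1 (1), 1 (4), 2 (7) | 31/132 = 23.5% | 19/132 = 14.4% |
| Month 2 | 0 (2), 2 (8), 3 (2) | 26/132 = 19.7% | 14/132 = 10.6% |
| Month 4 | 1 (3), 2 (1), 3 (5), 4 (3) | 16/132 = 12.1% | 7/132 = 5.3% |
| Month 6 | 2 (4), 3 (2), 4 (2), 5 (4) | 10/132 = 7.6% | 4/132 = 3.0% |
| Month 9 | 4 or more (12) | 0 | 0 |

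Calendar visits keep drifting later than the 30-day targets (Month 12: s = 365 + 1 − 360 = 6), so displacement is essentially nil from Month 9 on.

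**4. Effect on abnormal counts.** Share of abnormal by-visit values lost = share displaced × share of re-tests that are normal. The second factor is not in the documents; assume 20-80%.

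- 30-day months, ±5 days: 2/11 × 0.2 = 4% to 3/11 × 0.8 = 22%.
- 30-day months, ±7 days: 4/15 × 0.2 = 5% to 5/15 × 0.8 = 27%.
- Calendar months, Month 1: 19/132 × 0.2 = 3% to 31/132 × 0.8 = 19%. Month 6: 4/132 × 0.2 = 1% to 10/132 × 0.8 = 6%.

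**5. Effect on means.** A log-normal simulation of neutrophils (assumed median 3.5, between-subject log SD 0.4, within-subject log SD 0.35, limit 1.2, ±7 days centred on the target) moved the mean log value from 1.2528 to 1.2570. That is 0.0042, or about 0.4% of the geometric mean. Centring displaces 36% of flagged values, more than step 2 gives, so this is on the high side for those variances.

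**The case against.** The strongest reply is about timing. The protocol equates Month 72 with year 6 and calls Months 12, 24 and 36 annual visits, which points to calendar months. On that count the long-term tables, the purpose of this study, are untouched, and only Months 1, 2, 4 and 6 are exposed. This stands and is the main reason for the low priority. It does not remove the early visits, and the protocol does not define a month.

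Other points also stand. Results that meet the criteria in Protocol Sections 7.3.5 and 8.4 are recorded as AEs, whose incidence rates do not use the windows. The listings keep all values. Safety summaries follow the sponsor's data standards (Protocol Section 9.4), which are not shown and may already deal with repeats. A normal repeat may also be the truer value; but correcting only flagged results, and only when the visit was early, is not a consistent way to use it.

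A reader might infer that every by-visit laboratory display understates abnormality, and only in that direction. The documents do not support this. On-time and late draws are kept, and a re-test can be worse than the first value. Protocol Appendix 3 also says: "Unscheduled laboratory testing through the central laboratory may be obtained at any time during the study to assess such concerns". Such a draw could replace a normal scheduled value with an abnormal one.

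A reader might also count 4-week months and find more displacement. That does not fit the SAP: Month 24 would be Day 28 × 24 + 1 = 673, inside the Month 21 window (Days 586-675).

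**Conclusion.** The concern holds as a minor gap in the SAP. As written, the selection rule lets an abnormality-triggered re-test displace the abnormal scheduled value whenever the visit was early enough, so by-visit abnormality counts, shifts and extremes can be biased towards normal.

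For re-tests at 3-5 days, 18-27% (±5 days) or 27-33% (±7 days) of flagged values are displaced on 30-day months. On calendar months it is about 14-24% at Month 1, 11-20% at Month 2, 5-12% at Month 4, 3-8% at Month 6 and essentially none from Month 9. These figures rest on evenly spread visits and baseline on Day 1. The loss in abnormal counts also depends on an assumed share of normal re-tests.

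It would be tempting to conclude that the primary safety results are biased. The documents do not show that: the windows apply to by-visit displays, and the SAP leaves open which values feed the abnormality incidence endpoint. That silence is itself worth closing.

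**What to change.** Add to SAP Appendix 1: for by-visit laboratory displays, use the scheduled-visit sample whenever one exists in the window, and an unscheduled sample or re-test only if it is missing. Add to SAP Section 8.2.4: laboratory-abnormality incidence and worst-value tables use all on-treatment values, including re-tests.

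With this, no flagged scheduled value is displaced. The cost is two sentences and a sort key in the dataset program, with no new data. The re-testing rules in the protocol are not at fault and need no change for this purpose. The downside is that a spurious scheduled value stays in the by-visit table even when its repeat is normal; the listings show both.
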